16.33 Correlative Analyses

- 16.331 Minimal residual disease will be assessed on bone marrow aspirate in all patients achieving CR. The proportion of patients who achieve MRD negative status will be estimated by the number of patients who are MRD negative divided by the total number of evaluable patients who achieve an sCR or CR. Exact binomial 95% confidence intervals for the true MRD negative rate will be calculated.

16.4 Early Safety Analysis

An early safety analysis will be performed after the first 6 patients have been accrued to the study and observed for one cycle. Accrual will be temporarily halted while these patients are evaluated. If 2 or more of the first 6 patients experience a DLT as defined below, then accrual to the study will continue to be temporarily halted while the study team determines if changes to the dosing schedule are warranted.

Toxicity will be measured per NCI-CTCAE version 4. DLT is defined as an adverse event occurring during the first cycle of treatment that is possibly, probably, or definitely related to study treatment and that meets one of the following:

- Grade 3 diarrhea, nausea, and fatigue lasting > 3 days despite optimal supportive medications
- Any other \geq Grade 3 non-hematological toxicity with the exceptions of electrolyte abnormalities that are reversible and asymptomatic
- Febrile neutropenia
- Grade 3 thrombocytopenia with clinically significant bleeding
- Any \geq Grade 4 neutrophil count decreased or platelet count decreased that persists >7 days

16.5 Data & Safety Monitoring:

16.51 The principal investigator(s) and the study statistician will review the study at least twice a year to identify accrual, adverse event, and any endpoint problems that might be developing. The Mayo Clinic Cancer Center (MCCC) Data Safety Monitoring Board (DSMB) is responsible for reviewing accrual and safety data for this trial at least twice a year, based on reports provided by the MCCC Statistical Office.

16.52 Adverse Event Stopping Rules: The stopping rules specified below are based on the knowledge available at study development. We note that the Adverse Event Stopping Rule may be adjusted in the event of either (1) the study re-opening to accrual or (2) at any time during the conduct of the trial and in consideration of newly acquired information regarding the adverse event profile of the treatment(s) under investigation. The study team may choose to suspend accrual because of unexpected adverse event profiles that have not crossed the specified rule below.

Accrual will be temporarily suspended to this study if at any time we observe events considered at least possibly related to study treatment (i.e. an adverse event with attribute specified as “possible,” “probable,” or “definite”) that satisfy one of the following:

- if 5 or more patients in the first 15 treated patients experience a grade 4 or higher non-hematologic adverse event at least possibly related to treatment.
- if after the first 15 patients have been treated, 30% of all patients experience a grade 4 or higher non-hematologic adverse event at least possibly related to treatment.

We note that we will review grade 4 and 5 adverse events deemed “unrelated” or “unlikely to be related”, to verify their attribution and to monitor the emergence of a previously unrecognized treatment-related adverse event.

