Data from ongoing blinded pivotal trials (C16010) are not included.

a Note that rash maculopapular and rash macular represent the two most common terms used to describe rash

The clinical experience with ixazomib also shows early signs of antitumor activity as evidenced by at least a 50% reduction in disease burden in some patients and prolonged disease stabilization in others across all ongoing trials. The antitumor activity has been seen with single-agent ixazomib, when combined with established therapies, and across the malignancies studied (advanced solid tumors, non-Hodgkin's disease, Hodgkin's disease, relapsed and/or refractory multiple myeloma, relapsed or refractory systemic light chain amyloidosis, and newly diagnosed multiple myeloma) to date. (Kumar et al. 2014, Kumar et al. 2014, Kumar et al. 2014, Richardson et al. 2014)

1.5 **Pomalidomide:** Pomalidomide, a thalidomide analogue, is an immunomodulatory agent that displays similar anti-angiogenic activity, but far greater anti-proliferative and immunomodulatory activity compared to the parent drug. Pomalidomide has also been shown to stimulate antibody-dependent cytotoxic T-cell activity (ADCC).

The efficacy of pomalidomide in relapsed myeloma has been shown in multiple trials. (Streetly et al. 2008, Lacy et al. 2009, Lacy et al. 2010, Lacy et al. 2011, San Miguel et al. 2013, Leleu et al. 2015) At tolerated doses (MTD=2 mg QD and 5 mg QOD), pomalidomide has been shown to be active in subjects with relapsed or refractory multiple myeloma (MM) (study CC-4047-00-001). In 45 subjects who received doses of pomalidomide ranging, by cohort, up to 10 mg daily, the most commonly occurring dose-limiting toxicity (DLT) was reversible neutropenia. As with other IMiDs administered to

subjects receiving concomitant systemic steroids, deep vein thrombosis (DVT) was seen (in 1 subject each in this study and in its subsequent named patient supply rollover program).

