10.6 Required routine reporting

Adverse events to be graded at each evaluation and pretreatment symptoms/conditions to be evaluated at baseline per the CTCAE v4.0 grading unless otherwise stated in the table below:

SYSTEM ORGAN CLASS	Adverse event/Symptoms	Baseline	Each evaluation
Investigations	Creatinine increased	X	X
	Neutrophil count decreased	X	X
	Platelet count decreased	X	X
General disorders and administration site conditions	Fatigue	X	X
Gastrointestinal Disorders	Nausea	X	X
	Vomiting	X	X
	# of Stools	X	
	Diarrhea		X
	Constipation		X
Infections and infestations	Sepsis	X	X
Blood and lymphatic system disorders	Febrile neutropenia	X	X
Skin and subcutaneous tissue disorders	Rash, maculopapular	X	X
Nervous system disorders	Peripheral sensory neuropathy	X	X
	Peripheral motor neuropathy	X	X

10.62 Submit via appropriate MCCC Case Report Forms (i.e., paper or electronic, as applicable) the following AEs experienced by a patient and not specified in Section 10.5:

10.621 Grade 2 AEs deemed *possibly, probably, or definitely* related to the study treatment or procedure.

10.622 Grade 3 and 4 AEs regardless of attribution to the study treatment or procedure.

10.623 Grade 5 AEs (Deaths)

- Any death within 30 days of the patient's last study treatment or procedure regardless of attribution to the study treatment or procedure.
- Any death more than 30 days after the patient's last study treatment or procedure that is felt to be at least possibly treatment related must also be submitted as a Grade 5 AE, with a CTCAE type and attribution assigned.

10.63 Refer to the instructions in the Forms Packet (or electronic data entry screens, as applicable) regarding the submission of late occurring AEs following completion of the Active Monitoring Phase (i.e., compliance with Test Schedule in Section 4.0).

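### After the 6-patient review, the only mandatory accrual pause (16.52) leaves out related deaths coded as hematologic and weighs any other related death like a single Grade 4 event

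*Combined protocol and SAP*

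**What the plan says.** Section 16.52 opens with a mandatory clause: "Accrual will be temporarily suspended to this study if at any time we observe events considered at least possibly related to study treatment" and one of two bullets is met. The first bullet applies "if 5 or more patients in the first 15 treated patients experience a grade 4 or higher non-hematologic adverse event" that is at least possibly related. The second applies after 15 patients, if "30% of all patients experience a grade 4 or higher non-hematologic adverse event at least possibly related to treatment". Neither bullet has a hematologic limb or a separate limb for Grade 5, and the word non-hematologic is not defined.

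The documents do show how they sort the events in question:

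- The routine reporting table in 10.6 reads "Blood and lymphatic system disorders Febrile neutropenia", and Table 8.3 uses the same class. The 10.6 table puts sepsis under infections.
- The DLT list in 16.4 names febrile neutropenia, thrombocytopenia with bleeding, and prolonged Grade 4 neutrophil or platelet decreases separately from non-hematological toxicity.
- Section 1.5 counts anemia, thrombocytopenia and neutropenia as hematologic toxicity, and pneumonia as non-hematological.

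The other mandatory safety rule, in 16.4, covers Cycle 1 events in the first six patients: "If 2 or more of the first 6 patients experience a DLT as defined below, then accrual to the study will continue to be temporarily" stopped. Below the 16.52 thresholds suspension is optional: "The study team may choose to suspend accrual because of unexpected adverse event profiles that have not crossed the specified rule below". Sections 13.5, 16.214 and 16.25 give further discretion.

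**The concern.** By setting its grade limit at 4 or higher, the rule plainly means to include deaths. Leaving expected Grade 4 blood counts out of the tally is sensible for this combination, but the same limit also removes Grade 5 hematologic events. Febrile neutropenia is thus a DLT for the first six patients and then drops out of the mandatory count for the rest of the trial, even when it is fatal.

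The documents make myelosuppression foreseeable. Section 1.5 says of pomalidomide that "the most commonly occurring dose-limiting toxicity (DLT) was reversible neutropenia" and reports Grade 3 or 4 neutropenia in 35% of 60 patients given pomalidomide with dexamethasone. Section 15.27 lists both febrile neutropenia and neutropenic sepsis.

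Two things are at stake. First, whether a related death in a neutropenic patient counts may depend on the term chosen on the form. Second, 16.214 gives this rule as one of its two reasons, with the small sample size, for not halting accrual at the interim analysis.

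**Working it through.** **Plan's own figure.** The documents state no operating characteristics for 16.52, so there is none to reproduce.

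**Inputs from 16.52.** Threshold 5 of the first 15 treated patients; then 30% of all patients. The event rates below are assumptions, because the documents give none for related deaths.

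**Step 1: what is counted.** Take one related death in a neutropenic patient.

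| Term recorded | Class in the documents | Counts in 16.52? |
|---|---|---|
| Febrile neutropenia | Blood and lymphatic (10.6, Table 8.3); apart from non-hematological (16.4) | No |
| Cytopenia | Apart from non-hematological (16.4); hematologic (1.5) | No |
| Sepsis | Infections (10.6) | Yes |
| Pneumonia | Non-hematological (1.5) | Yes |

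**Step 2: four deaths in 15.** With four related non-hematologic deaths and no other qualifying patient, 4/15 = 26.7%. This is below the count of 5 and also below 30%. Later, 8/27 = 29.6% is still below 30%.

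**Step 3: probability that the first-15 rule stays silent.** With X the number of qualifying patients, X ~ Binomial(15, p), and silence is P(X ≤ 4) = Σ C(15,k) p^k (1−p)^(15−k) for k = 0 to 4. At p = 0.10 the terms are 0.2059 + 0.3432 + 0.2669 + 0.1285 + 0.0428 = 0.987.

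| Total qualifying rate p | P(silent) |
|---|---|
| 10% | 0.987 |
| 15% | 0.938 |
| 20% | 0.836 |
| 25% | 0.687 |

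The first three rows describe deaths alone if no other patient has a Grade 4 non-hematologic event. The last row shows what happens when other events add to the tally, for example 10% deaths plus a further 15% of patients with Grade 4 events.

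**Step 4: how far 16.4 helps.** If four deaths fall at random among 15 patients, the chance that at least two are in the first six is [C(6,2)C(9,2) + C(6,3)C(9,1) + C(6,4)] / C(15,4) = (540 + 180 + 15)/1365 = 0.54. This is an upper limit for 16.4 being met by those deaths, because each must also arise from a Cycle 1 event.

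**Step 5: effect of counting hematologic Grade 5 events.** Suppose 2% of patients (assumed) have such an event and no other qualifying event. The probability of reaching 5 of 15 rises from 0.013 to 0.027 if the base rate is 10% (10% to 12%), and from 0.164 to 0.220 if it is 20% (20% to 22%).

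**The case against.** A reader might infer that deaths with febrile neutropenia can never count. The documents do not support that. A death recorded as sepsis or pneumonia counts, no section says how fatal neutropenic infection is to be coded, and febrile neutropenia in Cycle 1 counts in the first six patients.

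A reader might also infer that four deaths in 15 would bring no pause of any kind. That is true only of 16.52. The 16.4 halt could be prolonged, and the team may suspend under 13.5, 16.214, 16.25 or 16.52. The DSMB reviews safety at least twice a year; at 1–2 patients a month, 15 patients take 7.5–15 months, so at least one review should fall in that time. Deaths within 30 days of the last dose, and later related deaths, are reported within 24 hours.

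Nor do the documents show that fatal myelosuppression is the leading lethal risk. Section 1.5 calls the neutropenia reversible, and 9.9c describes it as manageable. A pooled Grade 4-or-higher rule with discretion below the threshold is a coherent design.

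All of this limits the point but does not remove it. The 24-hour report carries no pause, and the discretionary clause in 16.52 concerns unexpected profiles, which a known toxicity may not be. The extra check of Grade 4 and 5 events in 16.52 is confined to those judged unrelated or unlikely to be related. After the 6-patient Cycle 1 review, no mandatory tally includes a related death coded as hematologic.

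**Conclusion.** The point holds in limited form. After the 16.4 review, the mandatory tally omits related deaths coded as febrile neutropenia or cytopenia, so it can depend on the coding term. Any other related death weighs the same as one Grade 4 event, and four in the first 15 do not cross the rule unless other qualifying events add to them.

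The silence probabilities of 99%, 94% and 84% are worst cases that rest on assumed death rates of 10%, 15% and 20% and on no other qualifying event; at a total qualifying rate of 25% the figure is 69%. The gap is in what obliges a pause, since the power to suspend exists throughout. It deserves correction because the correction is cheap and the rule is one of the grounds for continuing accrual through the interim.

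**What to change.** In both bullets of 16.52, replace the counted event with: *a Grade 4 non-hematologic adverse event, or any Grade 5 adverse event (hematologic or non-hematologic), at least possibly related to treatment*. A related death then counts whatever term is recorded.

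The cost is a change of wording and a rule that is crossed somewhat more often (step 5 gives the scale), with the added crossings arising from treatment-related deaths. No new data are needed.

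This change does not alter the four-deaths example: four non-hematologic deaths still total four. As an option, the sponsor could have each related Grade 5 event prompt a documented review by the study chair, statistician and DSMB, with any suspension of accrual left to that review. A compulsory suspension after every related death is a trade-off and is not needed for this point: at an assumed background related-death rate of 1–3%, the chance of at least one pause in 30 patients would be 1 − 0.99^30 = 26% to 1 − 0.97^30 = 60%.

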16.6 Results Reporting on ClinicalTrials.gov

At study activation, this study will have been registered within the “ClinicalTrials.gov” website. The Primary and Secondary Endpoints along with other required information for this study will be reported on www.ClinicalTrials.gov. For purposes of timing of the Results Reporting, the initial estimated completion date for the Primary Endpoint of this study is 2.5 years after the study opens to accrual. The definition of “Primary Endpoint Completion Date” (PECD) for this study is at the time the last patient registered has been followed for at least 6 months.

16.7 Inclusion of Women and Minorities

16.71 This study will be available to all eligible patients, regardless of race, gender, or ethnic origin.

- 16.72 There is no information currently available regarding differential effects of this regimen in subsets defined by race, gender, or ethnicity, and there is no reason to expect such differences to exist. Therefore, although the planned analysis will, as always, look for differences in treatment effect based on racial and gender groupings, the sample size is not increased in order to provide additional power for subset analyses.
- 16.73 The geographical region served by MCCC has a population which includes approximately 3% minorities. Based on prior MCCC studies involving similar disease sites, we expect about 3-5% of patients will be classified as minorities by race and about 33% of patients will be women. Expected sizes of racial by gender subsets are shown in the following table:

Accrual Estimates by Gender/Ethnicity/Race

Ethnic Category	Sex/Gender			
	Females	Males	Unknown	Total
Hispanic or Latino	0	1	0	1
Not Hispanic or Latino	10	19	0	29
Ethnic Category: Total of all subjects*	10	20	0	30
Racial Category				
American Indian or Alaskan Native	0	0	0	0
Asian	0	0	0	0
Black or African American	1	1	0	2
Native Hawaiian or other Pacific Islander	0	0	0	0
White	9	19	0	28
Racial Category: Total of all subjects*	10	20	0	30

Ethnic Categories: **Hispanic or Latino** – a person of Cuban, Mexican, Puerto Rico, South or Central American, or other Spanish culture or origin, regardless of race. The term “Spanish origin” can also be used in addition to “Hispanic or Latino.”

Not Hispanic or Latino

Racial Categories: **American Indian or Alaskan Native** – a person having origins in any of the original peoples of North, Central, or South America, and who maintains tribal affiliations or community attachment.

Asian – a person having origins in any of the original peoples of the Far East, Southeast Asia, or the Indian subcontinent including, for example, Cambodia, China, India, Japan, Korea, Malaysia, Pakistan, the Philippine Islands, Thailand, and Vietnam. (Note: Individuals from the Philippine Islands have been recorded as Pacific Islanders in previous data collection strategies.)

Black or African American – a person having origins in any of the black racial groups of Africa. Terms such as “Haitian” or “Negro” can be used in addition to “Black or African American.”

Native Hawaiian or other Pacific Islander – a person having origins in any of the original peoples of Hawaii, Guam, Samoa, or other Pacific Islands.

White – a person having origins in any of the original peoples of Europe, the Middle East, or North Africa.

17.0 Pathology Considerations/Tissue Biospecimens

None

18.0 Records and Data Collection Procedures

18.1 Submission Timetable

Data submission instructions for this study can be found in the Case Report Form packet.

18.2 Event monitoring

See Section 4.2 for the event monitoring schedule.

18.3 CRF completion for non-Mayo Clinic sites

This study will use Medidata Rave for remote data capture (rdc) of all study data.

18.4 Site responsibilities

Each co-sponsor/participant will be responsible for insuring that all materials contain the patient's initials, MCCC registration number, and MCCC protocol number. Patient's name must be removed.

18.5 Supporting documentation

This study requires supporting documentation for diagnosis and progression prior to study entry as well as for evidence of response to study therapy and progression after study therapy. Supporting documentation for diagnosis will include either a pathology report or a laboratory report demonstrating multiple myeloma with extramedullary disease or plasma cell leukemia (including bone marrow biopsy report; and SPEP, UPEP, FLC, FISH, and Cytogenetics reports). These reports should be submitted within 14 days of registration.

For progression of disease prior to study entry, supporting documentation includes the evidence needed to determine the patient's progression prior to enrollment. These documents should be submitted within 14 days of registration.

For response to treatment, supporting documentation includes SPEP, UPEP, FLC, Serum and Urine Immunofixation, Bone Marrow Biopsy and aspirate, and X-ray skeletal survey.

For patients who progress after study therapy supporting documentation may include any of the following: SPEP, UPEP, FLC, Serum and Urine Immunofixation, Bone Marrow Biopsy and aspirate, and X-ray skeletal survey.

18.6 Labelling of materials

Each site will be responsible for insuring that all materials contain the patient's initials, MCCC registration number, and MCCC protocol number. Patient's name must be removed.

18.7 Incomplete materials

Any data entered into a form will result in that form being marked as "received." However, missing data will be flagged by edit checks in the database.

18.8 Overdue lists

The list of overdue materials is available in the database at any time. A list of overdue materials and forms for study patients will be generated monthly. The listings will be sorted by location and will include the patient study registration

number. The appropriate co-sponsor/participant will be responsible to obtain the overdue material.

18.9 Corrections forms

If a correction is necessary the QAS will query the site. The query will be sent to the appropriate site to make the correction in the database and respond back to the QAS.

Appendix I ECOG Performance Status

ECOG PERFORMANCE STATUS*	
Grade	ECOG
0	Fully active, able to carry on all pre-disease performance without restriction
1	Restricted in physically strenuous activity but ambulatory and able to carry out work of a light or sedentary nature, e.g., light house work, office work
2	Ambulatory and capable of all selfcare but unable to carry out any work activities. Up and about more than 50% of waking hours
3	Capable of only limited selfcare, confined to bed or chair more than 50% of waking hours.
4	Completely disabled. Cannot carry on any selfcare. Totally confined to bed or chair.
5	Dead

*As published in Am. J. Clin. Oncol.:

The ECOG Performance Status is in the public domain therefore available for public use. To duplicate the scale, please cite the reference above and credit the Eastern Cooperative Oncology Group, Robert Comis M.D., Group Chair.

From [REDACTED]

Appendix II Patient Medication Diary

Name _____ Study ID Number _____

Please complete this diary on a daily basis. Write in the amount of the dose of pomalidomide, ixazomib, and dexamethasone that you took in the appropriate “Day” box.

On the days that you do not take any study drug, please write in “0”. If you forget to take your daily dose, please write in “0”, but remember to take your prescribed dose at the next regularly scheduled time.

Please drink at least 6 to 8 cups of liquid per day to help drug absorption. Swallow pills whole, with water, and do not to break, chew, crush or open the pills. Study drug should be taken on an empty stomach (no food or drink) at least 1 hour before or 2 hours after a meal. Each pill should be swallowed separately with a sip of water. A total of approximately 8 ounces (240 mL) of water should be taken with the pills.

If you experience any health/medical complaints or take any medication other than pomalidomide, ixazomib, or dexamethasone, please record this information.

Week of: _____

Study Drug	Day 1	Day 2	Day 3	Day 4	Day 5	Day 6	Day 7
Pomalidomide							
Ixazomib							
Dexamethasone							

Week of: _____

Study Drug	Day 8	Day 9	Day 10	Day 11	Day 12	Day 13	Day 14
Pomalidomide							
Ixazomib							
Dexamethasone							

Week of: _____

Study Drug	Day 15	Day 16	Day 17	Day 18	Day 19	Day 20	Day 21
Pomalidomide							
Ixazomib							
Dexamethasone							

Week of: _____

Study Drug	Day 22	Day 23	Day 24	Day 25	Day 26	Day 27	Day 28
Pomalidomide							
Ixazomib							
Dexamethasone							

Patient Signature: _____

My next scheduled visit is: _____
 If you have any questions, please call: _____
 Bring *all* bottles and any unused study medication along with this diary when you return for your next appointment.

Study Coordinator Use Only		
Number of pills returned	Number of vials returned:	
Discrepancy Yes ___/No ___	Verified by _____	Date _____

